# ABBREVIATIONS

ABBREVIATION DEFINITION

AE Adverse Event

ALD Assistive Listening Device

Cl Chief Investigator

CNC Consonant-Nucleus-Consonant

CPIB Communicative Participation Item Bank

CRF Case Report Form

eCRF electronic Case Report Form

GCP Good Clinical Practice
GP General Practitioner

HRA Health Research Authority ICF Informed Consent Form

IOI-HA International Outcomes Inventory Hearing

ISF Investigator Site File

LIFE-H Assessment of Life Habits

LiSN-S Listening in Specialised Noise-Sentences

MFIS Modified Fatigue Impact Scale

NHS National Health Service

NMDAS Newcastle Mitochondrial Disease Adult Scale

PA Physical Activity

PI Principal Investigator

PIS Participant Information Sheet
PPI Patient and Public Involvement
R&D Research & Development
PEC Passarch Ethics Committee

REC Research Ethics Committee
SAE Serious Adverse Event
SLA Service Level Agreement

SOP Standard Operating Procedure

SPaRQ Social Participation Restrictions Questionnaire SOS-HEAR Significant Other Scale for Hearing Disability SSQ Speech, Spatial & Qualities of Hearing Scale

SUS System Usability Scale

SUSAR Suspected Unexpected Serious Adverse Reaction

TMF Trial Master File

WCMR Wellcome Centre for Mitochondrial Research
WHOQOL-BREF World Health Organisation Quality of Life-BREF

QoL Quality of Life

# **TRIAL SUMMARY**

Trial Title	EMERALD Pilot study: E valuating the Tolerability and E fficacy of					
	a Remote Microphone (Assisted Listening Device) in Adults					
	Patients with Mitochondrial Disease					
Short Title/Acronym	EMERALD					
Summary of Design	Prospective, single centre, feasibility trial consisting of two					
	phases: (1) Four-week, randomised, AB/BA crossover trial and (2)					
	follow-on observational extension trial over 20 weeks (24 weeks					
	in total).					
	Participants will be randomly allocated (1:1 ratio) to one of two					
	sequences:					
	- Group 1: Aided with the device (2 weeks), followed by usual					
	care (non-aided) (2 weeks); or					
	- Group 2: Non-aided (2 weeks), followed by aided with the device					
	(2 weeks).					
Summary of Participant	Adults (16 to 70 years) with a proven genetic diagnosis of					
Population	mitochondrial disease and reported mild to severe hearing loss.					
	Partners/caregivers/close family members of included patients will					
	also be involved, as we are interested in assessing the potential					
	impact on caregiver burden.					
Planned Sample Size	It is anticipated that N=24 patients with mitochondrial disease and					
	reported hearing loss will need to be screened for N=12 eligible					
	participants to be recruited to the trial (i.e., to meet the pre-specified					
	eligibility criteria). This allows for trial completion by N=10					
	participants, allowing that approximately N=2 participants will					
	withdraw.					
Per Participant	24 weeks					
Duration						
Proposed Overall	12 months					
Duration						
Objective	Investigate the feasibility, tolerability and efficacy of a remote					
	microphone assistive listening device (ALD) in adult participants					
	with mitochondrial disease-related hearing loss.					

Sponsor Ref: 10224, IRAS ID 316557 EMERALD Protocol V3.1, 2023-12-04

# BACKGROUND

Mitochondrial diseases are the most common group of genetic neurological disorders, affecting one in every 4,300 individuals in the UK and are a major problem for both patients and society because of the high level of suffering and associated disability. Hearing loss and deafness both in isolation (non-syndromic) and as a feature of systemic mitochondrial disease (syndromic) is common, affecting between 50 - 80% of all cases at some time in the course of the disease.

Sound amplification by hearing aid remains the mainstay of symptomatic treatment. While hearing aids intensify sounds, unfortunately they do not enhance sound i.e., spoken word clarity.

Our pilot data suggest that impaired sound detection and/or auditory processing is the primary defect in mitochondrial disease-related hearing loss, limiting the effectiveness of hearing aids. Mitochondrial disease patients often report dissatisfaction or poor compliance, with the inability of a hearing aid to correct signal (sound) distortion with far-reaching implications on communication, psychological health, and quality of life (QoL).

Advances in technology have seen the rapid development of Assistive Listening Devices (ALDs) that can ameliorate communication and understanding difficulties for individuals with varying degrees of hearing loss and auditory processing deficits.

Novel remote microphone ALD systems, which can be used to enhance conventional hearing aids or can be stand-alone, employ wireless sound transmission to optimize the auditory signal by improving the signal-to-noise ratio for the user i.e., increasing the speaker's voice relative to background noise and thereby enhancing the user's ability to effectively understand speech.

Short term interventional studies (including by [name] et al. (Co-I)) have demonstrated the effects of ALDs in improving functional hearing in everyday listening situations.

No trial has examined the tolerability and efficacy of what appears to be an innovative treatment strategy for mitochondrial disease-related hearing impairment.

# TRIAL AIM

This pilot trial aims to explore the feasibility of the Phonak Roger On™ remote microphone, as an ALD in adults with mitochondrial disease hearing loss. This trial also aims to explore the far-reaching benefits to communication, social participation, and wellbeing, from ALD use.

# **OBJECTIVES & OUTCOME MEASURES**

The **primary** trial objective is to:

 Evaluate the tolerability and usability of a remote microphone ALD in adults with mitochondrial disease hearing loss throughout the trial period of 24 weeks.

This will be assessed via:

- Investigator designed questionnaire of tolerability, acceptability and satisfaction.
- Validated questionnaires on usability and hearing aid satisfaction, if applicable, (System Usability Scale and International Outcomes Inventory Hearing), respectively.
- Compliance (participant reports of daily device use and setting of use).
- Device related adverse effects and undesirable effects (including technical issues).
- Participant withdrawal number and reason(s) for trial withdrawal.

#### The **Secondary** trial objective is to:

• Explore the efficacy of a remote microphone ALD in adults with mitochondrial disease hearing loss.

This will be measured by the following assessments\* (results from Baseline will be compared with results from various points throughout the trial period):

- Consonant-Nucleus-Consonant (CNC) test
- Listening in Spatialised Noise-Sentences test (LiSN-S)
- Speech, Spatial and Qualities of Hearing Scale Short Form (SSQ-12) (participant selfrated)
- Communicative Participation Item Bank (CPIB) (participant self-rated)
- Significant Other Scale for Hearing Disability (SOS-HEAR) (caregiver rated)
- Assessment of Life Habits (LIFE-H- Short Form) (participant self-rated)
- Social Participation Restrictions Questionnaire (SPaRQ) (participant self-rated)
- World Health Organisation Quality of Life-BREF (WHOQOL-BREF) (participant self-rated)
- Modified Fatigue Impact Scale (MFIS) (participant self-rated)

Sponsor Ref: 10224, IRAS ID 316557 EMERALD Protocol V3.1, 2023-12-04

\* Further details of the assessments are included in Table 1

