#### 1) Four-week randomised, AB/BA crossover trial

Participants will be randomly allocated (1:1 ratio) to one of two sequences:

- Group 1: ALD-Aided (2 weeks), followed by usual care (non-ALD-Aided)
   (2 weeks); or
- o Group 2: Non-ALD-Aided (2 weeks), followed by ALD-Aided (2 weeks)

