#### 2) Follow-on observational trial extension over 20 weeks

All participants will use the ALD for a period of 20 weeks following the end of the crossover period.

This means that the trial duration per participant will be 24 weeks in total.

It is anticipated that a minimum of 24 patients with mitochondrial disease and self-reported hearing loss will be screened in order to recruit 12 eligible participants (based on our previous findings as well as published studies reporting hearing loss and auditory processing deficits in patients with mitochondrial disease). Accounting for ~10% attrition (if two participants withdraw from the trial), this will allow for the trial to be completed by ten participants.

In total, participants will attend for four visits:

- Screening / Baseline, to be completed on the same day (at both Newcastle University and NE1Hear)
- Week 2 (NE1Hear)
- Week 4 (NE1Hear)
- Week 24 (NE1Hear and Newcastle Hospitals)

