# **SCHEDULE OF EVENTS**

Trial Assessments	Visit 1 (Trial site)		Visit 2 (Site)	Visit 3 (Site)	Follow up (Remote)	Visit 4 (Site)	Withdrawal Visit (Site)	
	Screen	ing	Baseline		End of crossover/			, ,
	Newcastle University	Ne	e1Hear	Crossover	Start of observation	Observation	End of Trial	As applicable
	Week 0		Week 2 +/- 3 days	Week 4 +/- 3 days	Monthly +/- 7 days	Week 24 +/- 14 days		
Informed Consent	Х							
Medical History	Х						X	
Medication Review	Х						X	
NMDAS (or collection of results from existing NMDAS)	Х						X	
Demographics	Х						X	
Atkin & Fisher's Articulation Survey	Х							
Speech-in-noise (SiN) tests	Х							
Pure-tone-Audiometry	Х							
LiSN-S Test		Х					X	
Eligibility Confirmation		Х						
Re-confirm Consent			Х	X	Х	Х	X	
Assistive Listening Device (ALD) Fitted			X 	X 	X (1 & 2)			
CNC Test *			Х	X	Х		X	
Speech, Spatial & Qualities of Hearing Scale (SSQ-12)			Х	X	Х		X	X (†)
MFIS, CPIB, SPaRQ, LIFE-H (Short Form), WHOQOL-BREF, & SOS-HEAR ‡			Х				Х	X (†)
Randomisation			Х					
Tolerability Acceptability & Satisfaction Questionnaire, SUS, IOI-HA ‡				X	Х		X	X (†)
Review of any Adverse Events, Undesirable Effects & Technical Issues				X	Х	Х	X	X
Review of Diary Data (compliance)				X	Х	Х	X	X
Clinical review of medical notes/collect relevant clinical information			Х				X	
Technical Support (from research team and Phonak/Sonova)			Х	X	Х	Х	X	
Return ALD							X	Χ
Participant Feedback (optional)							Х	Χ

\* Completed in 2 conditions (ALD-Aided and non-ALD-Aided); test order randomly allocated to participants at Baseline and the same order repeated at each visit

 Group 1: ALD-Aided for the first 2 weeks (will have tolerability, usability and satisfaction reviewed at Week 2 visit and will record AEs and compliance for first 2 weeks)

 Group 2: Usual care (non-ALD-Aided) for the first 2 weeks (will have tolerability, usability and satisfaction reviewed at Week 4 visit and will record AEs and compliance from weeks 2-4)

(1 & 2) Group 2 who used the ALD in the preceding 2 weeks will continue to use the device, Group 1 will have the device re-fitted and commence use again

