#### Randomisation

A customised allocation list for participant allocation will be created (with provision of examples) and provided to the RECAP team for upload. Participants will be randomised in a 1:1 ratio, using variable length random permuted blocks (of size 2 and 4) in R statistical software by the trial statistician.

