# **STATISTICS**

Compliance, tolerability, satisfaction, experience and withdrawal data will primarily be summarised using descriptive statistics and/or visually.

Where appropriate, suitable mixed models may be used to explore longitudinal effects on these data (e.g., temporal within subject changes in compliance). The analysis of the secondary trial objectives efficacy outcome data) will be considered exploratory given the trial sample size.

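### The stated efficacy comparison, Baseline against later visits, does not use the randomised aided/non-aided contrast that the crossover provides

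*Protocol*

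**What the plan says.** The Protocol's secondary objective is to explore efficacy with nine measures: CNC, LiSN-S, SSQ-12, CPIB, SOS-HEAR, LIFE-H, SPaRQ, WHOQOL-BREF and MFIS. One parenthesis states the comparison for all of them: "results from Baseline will be compared with results from various points throughout the trial period". The Statistics section adds only that the efficacy analysis "will be considered exploratory given the trial sample size".

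Trial Design and Setting describes a randomised crossover: "Participants will be randomly allocated (1:1 ratio) to one of two sequences". The sequences are "Group 1: ALD-Aided (2 weeks), followed by usual care (non-ALD-Aided" and "Group 2: Non-ALD-Aided (2 weeks), followed by ALD-Aided (2 weeks", in each case for two weeks per period.

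The visit lists and the Schedule of Events show what is measured when:

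- **SSQ-12**: one score at each of Baseline, Week 2, Week 4 and Week 24.
- **CNC**: at the same four visits, "Completed in 2 conditions (ALD-Aided and non-ALD-Aided", in the same test order each time.
- **The other seven measures**: only at screening or Baseline and at Week 24 (optional questionnaires at withdrawal aside), after an extension in which everyone is meant to use the device.

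**The concern.** A crossover is run so that each participant is observed with and without the device, in randomised order, and trends over time cancel. The one comparison the Protocol states does not do this. Baseline is the first exposure to the SSQ-12 and CNC, and it is expected to fall on the same day as a long screening battery. A difference between Baseline and a later visit can therefore reflect practice, retest drift or fatigue as well as the device.

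At stake is the estimate that would inform a later trial. A before-after figure can suggest benefit where there is none, or understate a real benefit, while a controlled estimate is available from data already scheduled. Calling the analysis exploratory limits what may be claimed from it, but does not remove the bias.

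**Working it through.** **Inputs from the Protocol.** Recruitment: "will be screened in order to recruit 12 eligible participants". Two withdrawals are expected, so 12 − 2 = 10 completers. Allocation is 1:1, "using variable length random permuted blocks (of size 2 and 4". The Protocol states no efficacy effect size, SD or power, so there is no efficacy figure to reproduce.

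**Assumptions (not in the Protocol).** D = device effect, set to 1 so that results read as multiples of it. P = drift per two-week period, 0 or 0.3. c = share of D that persists after the device is returned, 0 or 0.5.

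**Step 1: sequence sizes.** With blocks of 2 and 4, the worst split at 12 is 7:5, when a block of 4 is cut after two like allocations: 5 + 2 = 7. In 20,000 simulated lists, about 89% were 6:6 and about 11% were 7:5 or 5:7.

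**Step 2: SSQ-12, change from Baseline pooled by visit.** With n1 in Group 1, n2 in Group 2 and N = n1 + n2:

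- Week 2 = (n1/N)D + P
- Week 4 = (n2/N)D + 2P + (n1/N)cD

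| Sequences | P | c | Week 2 | Week 4 | AB/BA contrast |
|---|---|---|---|---|---|
| 6:6 | 0 | 0 | 0.50 | 0.50 | 1.00 |
| 7:5 | 0 | 0 | 0.58 | 0.42 | 1.00 |
| 6:6 | 0.3 | 0 | 0.80 | 1.10 | 1.00 |
| 6:6 | 0 | 0.5 | 0.50 | 0.75 | 0.75 |

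The last column is half the difference between sequences in (Week 2 minus Week 4), which equals D(1 − c/2). P cancels. With D = 0, P = 0.3 and c = 0, the pooled changes are 0.30 and 0.60, and the contrast is 0.

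**Step 3: SSQ-12, change from Baseline by condition.** With 6:6 and c = 0, mean aided change is ((D + P) + (D + 2P))/2 = D + 1.5P. Mean non-aided change is (2P + P)/2 = 1.5P. With D = 1 and P = 0.3 these are 1.45 and 0.45. Nothing is halved, but each figure carries the drift. Only their difference, 1.00, is free of it, and that difference is the crossover contrast.

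**Step 4: CNC.** Let b be the immediate aided benefit, L the practice gain by a later visit and a any acclimatisation to the device.

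- Later aided minus Baseline aided = L + a; b has gone.
- Later non-aided minus Baseline non-aided = L.
- Later aided minus Baseline non-aided = b + L + a; practice is added.
- Aided minus non-aided at the same visit = b + a; practice cancels.

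**Step 5: precision of the SSQ-12 contrast.** With 10 completers at 5:5 and s the SD of the within-person difference, the variance is (1/4)(s²/5 + s²/5) = s²/10. The 95% half-width is t(8, 0.975) × s/√10 = 2.306/3.162 × s = 0.73s.

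**The case against.** The strongest reply is that the parenthesis sits in an objectives list, covers measures with different schedules and names no model. A statistical analysis plan, not available here, could specify treatment, period and sequence terms. A reader might infer that the plan throws the randomised comparison away. The Protocol does not say so: it states a different comparison and is silent on the crossover contrast. What remains is that the sentence is a positive statement, and an analysis plan should not have to overturn it.

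A reader might also infer that device effects will be halved across the efficacy measures. That is not supported. Halving needs pooling by visit, which the Protocol does not state. It can touch only SSQ-12, because CNC is scheduled in both conditions and seven of the nine measures have no Week 2 or Week 4 value. For those seven, before-after change is all the schedule allows.

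The crossover contrast has limits too. No washout is described, and with c = 0.5 it falls to 0.75. Participants know whether they have the device, so expectation stays in a self-rated aided-minus-non-aided difference. A useless device need not give zero. Both limits stand, and neither favours the Baseline comparison.

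**Conclusion.** The point holds in limited form. The Protocol's stated efficacy comparison does not use the contrast its design provides.

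- **SSQ-12**: the period effect enters in full on any Baseline comparison. The loss of about half the device effect is conditional on pooling by visit and on no carryover. The drift sizes are illustrations, because the Protocol gives none.
- **CNC**: the fault does not depend on pooling. Any cross-visit comparison either removes the immediate benefit or adds practice to it.
- **The other seven**: the comparison is unavoidable, and the label is what needs changing. LiSN-S needs particular care. An impaired score is one route to eligibility and the screening value is its only earlier value, so some regression to the mean is possible.

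It would be too strong to call this an essential correction. The primary objective, tolerability and usability, is untouched; efficacy is exploratory in a pilot of 12; and every value needed for the better estimate is already scheduled.

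**What to change.** Replace the parenthesis under the secondary objective, and add matching text to Statistics:

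- **(a) SSQ-12**: efficacy is the period-adjusted within-participant aided-minus-non-aided difference from Weeks 2 and 4 (the average of the two sequence-specific mean differences), with a 95% confidence interval. State that no washout is described, so carryover could bias it, and that unblinded self-rating leaves expectation in the estimate.
- **(b) CNC**: the aided-minus-non-aided difference within the same visit, separately in quiet and in noise.
- **(c) LiSN-S, MFIS, CPIB, SPaRQ, LIFE-H, WHOQOL-BREF and SOS-HEAR**: change from screening or Baseline to Week 24, reported as uncontrolled before-after change and not as evidence of device efficacy.

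IOI-HA stays under the primary objective, where the Protocol lists it. Item (b) needs CNC in both conditions from everyone. The asterisk on CNC in the Week 2 and Week 4 lists can be read as the footnote restricting items to the aided group, so it should be reconciled with the Schedule of Events.

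The cost is wording only, with no new visits, data or participants. If an analysis plan already specifies these contrasts, the Protocol sentence should be aligned with it. Settle this before the data are examined, since choosing a contrast after seeing results from 10 to 12 people would invite selection.

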**Table 1: Outcome Measures** 

Measure	Descriptors	Domain Assessed	
CNC test	Phonemically balanced word list presented in 2 listening situations (quiet & with noise). Phonetically imitated; percentage of correct phonemes (speech sounds) calculated 	Speech perception	
LiSN-S test	A Speech Reception Threshold is established in 4 conditions (vary in vocal differences & location to noise) to provide binaural assessment of speech perception (ability to segregate a target speech signal from background noise in a 3D-auditory environment) 	Spatial processing	
Tolerability, Acceptability & Satisfaction (Appendix 1)	7-point Likert scale designed to investigating perceived usefulness, ease of use and behaviour intention	Tolerability, Acceptability &	
Record of Adverse Events, Undesirable Effects &Technical Issues	Adverse Events, undesirable effects and technical issues will be reported by participants (to the trial team at all follow-ups and on an ad-hoc basis).	Satisfaction	
SUS (Appendix 2)	10-item Likert originally designed to measure perceived ease-of-use of a device or system/technology; also provides usability (8-items) &learnability (2-items) subscales.	Usability	
IOI-HA (Appendix 3)	7-item questionnaire designed to evaluate effectiveness of hearing aid treatments. This will be completed by participants who use hearing-aids.	Hearing-aid satisfaction	
Compliance Diary	Participant reported daily diary of ALD use, including setting (e.g., meeting, transport, telephone) and their perceived experience of ALD use in real-time	Compliance	
Number of participants who withdraw	The number of participants who are randomised but subsequently withdraw from the trial will be recorded. Reason/s for withdrawal and time-point details will be collected.	•	
NMDAS	Semi-quantitative, reproducible clinical rating scale of disease progression designed specifically for all forms of mitochondrial disease 	Disease burden	
SSQ-12 (Short Version) (Appendix 4)	12-item version of full SSQ (a subjective assessment of listening and hearing ability in a variety of situations encountered in everyday life) 	Subjective hearing/ listening ability	
CPIB (Appendix 5)	Verbal communication assessed in a range of interactions (46 items); validated and reliable PROMIS measure 	Communicative participation	
SOS-HEAR* (Appendix 6)	A 36-item five-point scale developed to quantify 3 rd party disability of hearing loss 	Caregiver burden	
LIFE-H Short Form (Appendix 7)	Shortened version of LIFE-H which is a psychometrically robust tool to assess daily activities & social participation (life habits), based on self-perceived level of difficulty & assistance required. 12T	Social participation	
SPaRQ (Appendix 8)	19-item assessment of participation restrictions, comprising Social Behaviours and Social Perceptions due to hearing loss 	Participation restriction	
WHOQOL-BREF (Appendix 9)	An international measure of QoL to evaluate overall perception of QoL and health 	Health-related QoL	
Modified FIS (Appendix 10)	21-items; assessing the perceived impact of fatigue on cognitive, physical & psychosocial function.  Modified version of the Fatigue Impact Scale 	Perceived fatigue impact	

Abbreviations: IOI-HA, International Outcomes Inventory Hearing; SUS, Systems Usability Scale.

\*completed by partners/caregivers/close family members (non-mandatory). Participants will still be eligible they do not have a partners/caregivers/close family member who is able or willing to participate.

# TRIAL DESIGN AND SETTING

This single-centre, prospective pilot trial will take place in tertiary care within the Newcastle upon Tyne NHS Hospitals Foundation Trust (Newcastle Hospitals). Wherever possible, participants will have their End of Trial visit coincide with their routine clinical visit to the Newcastle Mitochondrial Disease Clinic for Adults and Children.

Trial visits will also take place at the Newcastle University Medical School (Auditory Cognition Group) https://www.auditorycognition.org/ (Screening/Baseline only) and NE1Hear https://www.ne1hear.co.uk/, where participants will undergo auditory assessment and ALD device fitting by qualified audiologists. NE1Hear have been contracted by Newcastle Hospitals to provide NHS services and will provide hearing assessments for this trial as per a relevant SLA.

Data will be captured at site, at Newcastle University and by NE1Hear, and will also be captured remotely (i.e., participant questionnaires completed at home, or experience data completed in real-time in any setting). Data will be collated via the REDCAP electronic Case Report Form (eCRF) system.

This trial will consist of two phases:

